1.1 Title

Canagliflozin and Cardiovascular and Renal Events in Type 2 Diabetes ([CANVAS trial](#))

1.2 Intended aim(s)

To compare canagliflozin to placebo on cardiovascular (CV) events including CV death, heart attack, and stroke in patients with type 2 diabetes mellitus (T2DM), whose diabetes is not well controlled at the beginning of the study and who have a history of CV events or have a high risk for CV events.

1.3 Primary endpoint for replication and RCT finding

Major Adverse Cardiovascular Events, Including CV Death, Nonfatal Myocardial Infarction (MI), and Nonfatal Stroke

1.4 Required power for primary endpoint and noninferiority margin (if applicable)

With 688 cardiovascular safety events recorded across the trials, there would be at least 90% power, at an alpha level of 0.05, to exclude an upper margin of the 95% confidence interval for the hazard ratio of 1.3.

1.5 Primary trial estimate targeted for replication

HR = 0.86 (95% CI 0.75–0.97) comparing canagliflozin to placebo (Neal et al., 2017)

2. Person responsible for implementation of replication in Aetion

[name]. implemented the study design in the Aetion Evidence Platform. S/he is not responsible for the validity of the design and analytic choices. All implementation steps are recorded and the implementation history is archived in the platform.

[figure not shown]
3. Data Source(s)

United/Optum, MarketScan, Medicare

4. Study Design Diagram

The study design diagram visualizes key aspects of the longitudinal study design for expedited review.

Design Diagram – CANVAS TRIAL REPLICATION

5. Cohort Identification

5.1 Cohort Summary

This study will involve a new user, parallel group, cohort study design comparing canagliflozin to the DPP-4 inhibitor (DPP4i) antidiabetic class. DPP4is serve as a proxy for placebo, since this class of antidiabetic drugs is not known to have an impact on the outcome of interest. The comparison against DPP4 inhibitors is the **primary comparison**. Initiators of 2nd generation sulfonylureas are used as a secondary comparator group. The patients will be required to have continuous enrollment during the baseline period of 180 days before initiation of canagliflozin or a comparator drug (cohort entry date). Follow-up for the outcome (3P-MACE), begins the day after drug initiation. As in the trial, patients are allowed to take other antidiabetic medications during the study.

5.2 Important steps for cohort formation

5.2.1 Eligible cohort entry dates

Market availability of canagliflozin in the U.S. started on March 29, 2013.

- For Marketscan and Medicare: April 1, 2013-Dec 31, 2017 (end of data availability).
- For Optum: April 1, 2013-March 31, 2019 (end of data availability).

5.2.2 Specify inclusion/exclusion criteria for cohort entry and define the index date

Inclusion and exclusion criteria were adapted from the trial as closely as possible. Definitions for all inclusion/exclusion are provided in **Appendix A** and are summarized in the flowcharts below.

5.3 Flowchart of the study cohort assembly

For canagliflozin vs. DPP4i

	Optum		Marketscan		Medicare*	
	Less Excluded Patients	Remaining Patients	Less Excluded Patients	Remaining Patients	Less Excluded Patients	Remaining Patients
All patients		74,864,884		191,990,035		23,466,175

Patients who used exposure or a reference between April 1, 2013 to Dec 2017 (for Marketscan/Medicare)/March 2019 (for Optum)	-74,192,962	671,922	-191,172,811	817,224	-21,718,863	1,747,312
Patients who have continuous 6 months registration in the database	-89,308	582,614	-69,496	747,728	-466,595	1,280,717
Patients without prior use of reference	-339,732	242,882	-464,089	283,639	-810,370	470,347
Patients without prior use of exposure	-75,001	167,881	-89,428	194,211	-71,119	399,228
Excluded because patient qualified in >1 exposure category	-236	167,645	-312	193,899	-301	398,927
Excluded based on Age	-7	167,638	0	193,899	0	398,927
Excluded based on Gender	-8	167,630	0	193,899	0	398,927
Excluded based on Inclusion 1- DM Type 2 with ICD-10	-5,385	162,245	-9,472	184,427	-4,090	394,837
Excluded based on Inclusion 2- History or high risk of cardiovascular disease (with 180 day lookback)	-25,130	137,115	-39,753	144,674	-20,833	374,004
Excluded based on Inclusion 3- Include all males OR Female postmenopausal- >45 years of age OR use of contraceptives	-7	137,108	-9	144,665	0	374,004
Excluded based on Exclusion 1- DM Type I + Secondary DM + Diabetic ketoacidosis with ICD10 CODES	-4,572	132,536	-3,939	140,726	-16,980	357,024
Excluded based on Exclusion 4- History of one or more severe hypoglycemic episode- Severe hypoglycemia (Inpatient, primary)	-109	132,427	-47	140,679	-472	356,552
Excluded based on Exclusion 5- Glucose-galactose malabsorption/Primary Renal glucosuria	-37	132,390	-30	140,649	-173	356,379
Excluded based on Exclusion #7- Renal disease that requires treatment with immunosuppressive therapy	-1,512	130,878	-662	139,987	-6,367	350,012
Excluded based on Exclusion 8- MI, unstable angina, revascularization procedure, or cerebrovascular accident within 3 months	-2,345	128,533	-1,604	138,383	-8,548	341,464
Excluded based on Exclusion 9- Cardiac conduction disorder(inpatient)/Other cardiac dysrhythmia (inpatient)	-167	128,366	-71	138,312	-517	340,947
Excluded based on Exclusion 10- Liver disease	-2,303	126,063	-1,695	136,617	-6,089	334,858
Excluded based on Exclusion 11- Any history of or planned bariatric surgery (prior 5 years)	-22	126,041	-95	136,522	-12	334,846
Excluded based on Exclusion 14- History of Malignant Neoplasm (prior 5 years)	-4,554	121,487	-3,985	132,537	-19,311	315,535
Excluded based on Exclusion 15- HIV/AIDS (dx and meds) -prior 5 years	-64	121,423	-56	132,481	-127	315,408
Excluded based on Exclusion 16- Hematological disorder	-1,540	119,883	-1,633	130,848	-7,624	307,784
Excluded based on Exclusion 17- CCI (180 days) >=10	-177	119,706	-50	130,798	-696	307,088

Excluded based on Exclusion 18 - Major Surgery (90 days prior)	-191	119,515	-212	130,586	-674	306,414
Excluded based on Exclusion 20- Use of SGLT2i (prior 6 months)	-833	118,682	-892	129,694	-817	305,597
Excluded based on Exclusion 22- use of a corticosteroid medication or immunosuppressive agent	-3,235	115,447	-3,085	126,609	-8,985	296,612
Excluded based on Exclusion 23- Use of cana in prior 3 months (although this is already applied as part of cohort creation)	0	115,447	0	126,609	0	296,612
Excluded based on Exclusion 24- Alcohol or Drug abuse (prior 3 years) and Exclusion 25- Pregnancy	-972	114,475	-532	126,077	-1,766	294,846
Final cohort		114,475		126,077		294,846

* Medicare database includes only patients with at least one diagnosis for diabetes, heart failure, or cerebrovascular disease.

**Exclusion 24 and 25 collapsed to adhere to CMS cell suppression guidelines.

For canagliflozin vs. 2nd generation SUs

	Optum		MarketScan		Medicare*	
	Less Excluded Patients	Remaining Patients	Less Excluded Patients	Remaining Patients	Less Excluded Patients	Remaining Patients
All patients		74,864,884		191,990,035		23,466,175
Patients who used exposure or a reference between April 1, 2013 to Dec 2017 (for MarketScan/Medicare)/March 2019 (for Optum)	-73,662,096	1,202,788	-190,768,942	1,221,093	-20,351,733	3,114,442
Patients who have continuous 6 months registration in the database	-165,247	1,037,541	-115,162	1,105,931	-861,454	2,252,988
Patients without prior use of reference	-710,706	326,835	-759,153	346,778	-1,627,827	625,161
Patients without prior use of exposure	-70,933	255,902	-88,833	257,945	-68,783	556,378
Excluded because patient qualified in >1 exposure category	-168	255,734	-149	257,796	-118	556,260
Excluded based on Age	-10	255,724	0	257,796	0	556,260
Excluded based on Gender	-17	255,707	0	257,796	0	556,260
Excluded based on Inclusion 1- DM Type 2 with ICD-10	-14,479	241,228	-23,583	234,213	-8,608	547,652
Excluded based on Inclusion 2- History or high risk of cardiovascular disease (with 180 day lookback)	-38,807	202,421	-54,172	180,041	-30,020	517,632
Excluded based on Inclusion 3- Include all males OR Female postmenopausal- >45 years of age OR use of contraceptives	-21	202,400	-36	180,005	0	517,632

Excluded based on Exclusion 1- DM Type I + Secondary DM + Diabetic ketoacidosis with ICD10 CODES	-5,426	196,974	-4,290	175,715	-19,804	497,828
Excluded based on Exclusion 4- History of one or more severe hypoglycemic episode- Severe hypoglycemia (Inpatient, primary)	-76	196,898	-37	175,678	-332	497,496
Excluded based on Exclusion 5- Glucose-galactose malabsorption/Primary Renal glucosuria	-53	196,845	-55	175,623	-221	497,275
Excluded based on Exclusion #7- Renal disease that requires treatment with immunosuppressive therapy	-2,276	194,569	-976	174,647	-9,763	487,512
Excluded based on Exclusion 8- MI, unstable angina, revascularization procedure, or cerebrovascular accident within 3 months	-3,178	191,391	-2,244	172,403	-11,210	476,302
Excluded based on Exclusion 9- Cardiac conduction disorder(inpatient)/Other cardiac dysrhythmia (inpatient)	-240	191,151	-121	172,282	-837	475,465
Excluded based on Exclusion 10- Liver disease	-3,273	187,878	-2,251	170,031	-8,410	467,055
Excluded based on Exclusion 11- Any history of or planned bariatric surgery (prior 5 years)	-27	187,851	-109	169,922	-16	467,039
Excluded based on Exclusion 14- History of Malignant Neoplasm (prior 5 years)	-6,172	181,679	-5,306	164,616	-25,472	441,567
Excluded based on Exclusion 15- HIV/AIDS (dx and meds) -prior 5 years	-112	181,567	-72	164,544	-198	441,369
Excluded based on Exclusion 16- Hematological disorder	-1,925	179,642	-1,989	162,555	-9,438	431,931
Excluded based on Exclusion 17- CCI (180 days) >=10	-287	179,355	-50	162,505	-993	430,938
Excluded based on Exclusion 18 - Major Surgery (90 days prior)	-317	179,038	-291	162,214	-856	430,082
Excluded based on Exclusion 20- Use of SGLT2i (prior 6 months)	-904	178,134	-984	161,230	-874	429,208
Excluded based on Exclusion 22- use of a corticosteroid medication or immunosuppressive agent	-4,334	173,800	-3,909	157,321	-10,920	418,288
Excluded based on Exclusion 23- Use of cana in prior 3 months (although this is already applied as part of cohort creation)	0	173,800	0	157,321	0	418,288
Excluded based on Exclusion 24- Alcohol or Drug abuse (prior 3 years) and Exclusion 25- Pregnancy	-1566	172,234	-777	156,544	-2,592	415,696
Final cohort		172,234		156,544		415,696

* Medicare database includes only patients with at least one diagnosis for diabetes, heart failure, or cerebrovascular disease.

** Exclusion 24 and 25 collapsed to adhere to CMS cell suppression guidelines.

6. Variables

6.1 Exposure-related variables:

Study drug:

The study exposure of interest is initiation of canagliflozin. Initiation will be defined by no use of any SGLT-2 inhibitor or a comparator in the prior 6 months before treatment initiation (washout period).

Comparator agents:

- Initiators of canagliflozin will be compared to initiators of-
 - DPP4i (**primary**)
 - 2nd generation sulfonylureas

Because canagliflozin and comparators are frequently used as second or third line treatments of T2DM, we expect it to be unlikely that canagliflozin and comparators are initiated in patients with substantially different baseline risk for proposed outcomes.

6.2 Preliminary Covariates:

- Age
- Sex
- Combined Comorbidity Index (CCI), measured over the default baseline covariate assessment period, defined as 180 days prior to and including index date

Covariates listed above represent only a small subset of covariates that will ultimately be controlled for in the design and analysis. We use the covariates above only for initial feasibility analyses to judge whether there is likely to be sufficient overlap between treatment groups to proceed with the study. Remaining covariates are defined only after the study has passed the initial feasibility analysis and the initial power assessment and are listed in Table 1 (**Appendix B**). These covariates are based on those used by Patorno et al. (2019).

6.3 Outcome variables and study follow-up:

6.3.1 Outcome variables

Effectiveness outcomes of interest (definitions provided in **Appendix A**):

- **Primary outcome:** 3-point major adverse cardiovascular events (MACE), i.e., non-fatal myocardial infarction, non-fatal stroke, or CV mortality
- Secondary outcomes: Individual components:
 - Hospital admission for MI (for purposes of this individual component, fatal MI is included)
 - Hospital admission for stroke (for purposes of this individual component, fatal stroke is included)
 - All-cause mortality/CV mortality:
 - All-cause inpatient mortality identified using discharge status codes will be used as a proxy for “CV mortality” in commercial databases
 - Information on CV mortality through data linkage with the National Death Index (NDI) will only become available at a later date for Medicare and will be used in secondary analyses.

Control outcomes of interest (control outcomes only serve to assess aspects of study validity but are not further interpreted):

1. Diabetes Ketoacidosis (we expect to see a positive association; Neal et al., 2017)
2. Heart failure (we expect to see a protective effect; Neal et al., 2017)

Control outcome definitions

Outcome	Definition	Comments
Control Outcomes		
Diabetic Ketoacidosis	Inpatient ICD-9 diagnosis: 250.1x	Note- The corresponding ICD-10 codes will also be used
Heart Failure	Inpatient ICD-9 diagnosis (primary diagnosis): 428.x, 398.91, 402.01, 402.11, 402.91, 404.01, 404.11, 404.91, 404.03, 404.13, 404.93	Note- The corresponding ICD-10 codes will also be used

6.3.2 Study follow-up

Both as-treated (AT) and intention-to-treat (ITT) analyses will be conducted with treatment defined as the index drug on the day of cohort entry. Because adherence in the real world databases is expected to be much worse than in the trial, the AT analysis is the **primary** analysis, as it targets the relative hazard of outcomes on treatment.

For the AT analyses, the follow-up will start the day after initiation of canagliflozin and comparator and will continue until the earliest date of the following events:

- The first occurrence of the outcome of interest, unless otherwise specified for selected outcomes,

- The date of end of continuous registration in the database,
- End of the study period,
- Measured death event occurs,
- Nursing home admission
 - Nursing home admissions are considered a censoring event because the data sources utilized typically provide little to no data on a patient, particularly on drug utilization, after admission. We will utilize this as an exclusion reason for cohorts for the same reason.
- The date of drug discontinuation, defined as the date of the last continuous treatment episode of the index drug (canagliflozin and comparator) plus a defined grace period (i.e., 30 days after the end of the last prescription's days' supply in main analyses).
- The date of augmentation or switching from an exposure to a comparator or any other agent in the comparator class and vice versa (e.g. switching from saxagliptin to linagliptin would be a censoring event);
 - A dosage change on the index treatment does not fulfill this criterion
 - An added treatment that is not part of the exposure or comparator group does not fulfill this criterion (e.g. if a canagliflozin user adds insulin, he or she does not get censored at the time of insulin augmentation)

For the ITT analyses, the censoring based on the augmentation/switching and treatment discontinuation will be replaced with a maximum allowed follow-up time of 365 days.

7. Initial Feasibility Analysis

Action report name:

For canagliflozin vs. DPP4i

Optum- <https://bwh-dope.aetion.com/#/projects/details/660/results/26056/result/0>

Marketscan- <https://bwh-dope.aetion.com/#/projects/details/661/results/26057/result/0>

Medicare- <https://bwh-dope.aetion.com/#/projects/details/662/results/26055/result/0>

For canagliflozin vs. 2nd generation SUs

Optum- <https://bwh-dope.aetion.com/#/projects/details/660/results/26064/result/0>

Marketscan- <https://bwh-dope.aetion.com/#/projects/details/661/results/26065/result/0>

Medicare- <https://bwh-dope.aetion.com/#/projects/details/662/results/26066/result/0>

Date conducted: 09/30/2018

Complete Aetion feasibility analysis using age, sex, and CCI as the only covariates and the primary endpoint (Section 6.3.1) as the outcome. No measures of association will be computed nor will incidence rates stratified by treatment group.

- Report patient characteristics by treatment group
- Report summary parameters of the overall study population
- Report median follow-up time by treatment group
- Report reasons for censoring in the overall study population

8. Initial Power Assessment

Aetion report name:

- For canagliflozin vs. DPP4i
Optum- <https://bwh-dope.aetion.com/#/projects/details/660/results/26064/result/0>
Marketscan- <https://bwh-dope.aetion.com/#/projects/details/661/results/26065/result/0>
Medicare- <https://bwh-dope.aetion.com/#/projects/details/662/results/26066/result/0>
- For canagliflozin vs. 2nd generation Sus
Optum- <https://bwh-dope.aetion.com/#/projects/details/660/results/26067/result/0>
Marketscan- <https://bwh-dope.aetion.com/#/projects/details/661/results/26068/result/0>
Medicare- <https://bwh-dope.aetion.com/#/projects/details/662/results/26069/result/0>

Date conducted: 09/30/2018

In order to complete the initial power analysis, the dummy outcome of a 90-day gap in database enrollment will be used. This outcome is used to ensure that no information on the comparative risks of the outcomes of interest are available at this stage. Complete a 1:1 PS-matched comparative analysis using this outcome. PS should include only 3 covariates: age, sex, and combined comorbidity index. Power calculations are based on the formulas from Chow et al. (2008).

- Stop analyses until feasibility and power are reviewed by primary investigators and FDA. Reviewers evaluate the results of the analyses described above in Sections 7 and 8, including numbers of patients, patient characteristics, follow-up time, and reasons for censoring by treatment group, as well as overall rates of outcomes and study power. These parameters are re-evaluated and reported in the subsequent sections, after incorporating feedback and refining the protocol.

Reviewed by PI:	[name]	Date reviewed:	10/26/18
Reviewed by FDA:	[name]	Date reviewed:	12/11/18
Reasons for stopping analysis (if required):			

9. Balance Assessment after PS matching

Action report name:

For canagliflozin vs. DPP4i

- Optum- <https://bwh-dope.aetion.com/projects/details/660/results/44837/result/0>
- Marketscan- <https://bwh-dope.aetion.com/projects/details/661/results/44838/result/0>
- Medicare- <https://bwh-dope.aetion.com/projects/details/662/results/44839/result/0>

For canagliflozin vs. 2nd generation SUs

- Optum- <https://bwh-dope.aetion.com/projects/details/660/results/44834/result/0>
- Marketscan- <https://bwh-dope.aetion.com/projects/details/661/results/44835/result/0>
- Medicare- <https://bwh-dope.aetion.com/projects/details/662/results/44836/result/0>

Date conducted: 11/18/2019

After review of initial feasibility and power analyses, complete creation of the remaining covariates (see Table 1 below for list of covariates). Again, using the dummy outcome of a 90-day gap in database enrollment, complete a 1:1 PS-matched analysis. The PS should include the complete list of covariates (excluding laboratory values, which are missing in some patients).

- Provide plot of PS distributions stratified by treatment group.

Note- Please refer to **Appendix B**.

- Report covariate balance after matching.

Note- For Table 1, please refer to **Appendix B**.

- Report reasons for censoring by treatment group.

- For canagliflozin vs. DPP4i

	Overall	Referent	Exposure
Dummy Outcome	0 (0.00%)	0 (0.00%)	0 (0.00%)
Death	589 (0.39%)	374 (0.49%)	215 (0.28%)
Start of an additional exposure	6,913 (4.54%)	2,413 (3.17%)	4,500 (5.91%)
End of index exposure	98,215 (64.53%)	47,931 (62.98%)	50,284 (66.08%)
Specified date reached	22,353 (14.69%)	12,162 (15.98%)	10,191 (13.39%)
End of patient enrollment	19,170 (12.60%)	9,407 (12.36%)	9,763 (12.83%)
Switch to other DPP4i (for censoring) + nursing home admission	4,962 (3.26%)	3,814 (5.01%)	1,148 (1.51%)

- For canagliflozin vs. 2nd generation SUs

	Overall	Referent	Exposure
Dummy Outcome	0 (0.00%)	0 (0.00%)	0 (0.00%)
Death	548 (0.40%)	364 (0.53%)	184 (0.27%)
Start of an additional exposure	6,001 (4.36%)	1,842 (2.68%)	4,159 (6.04%)
End of index exposure	85,900 (62.38%)	41,024 (59.58%)	44,876 (65.18%)
Specified date reached	22,281 (16.18%)	12,957 (18.82%)	9,324 (13.54%)
End of patient enrollment	18,853 (13.69%)	9,660 (14.03%)	9,193 (13.35%)
Switch to other SUs (for censoring) + nursing home admission	4,117 (2.99%)	3,003 (4.36%)	1,114 (1.62%)

- Report follow-up time by treatment group.

- For canagliflozin vs. DPP4i

Median Follow-Up Time (Days) [IQR]			
Patient Group	Optum	MarketScan	Medicare
Overall Patient Population	127 [58-306]	149 [72-341]	147 [81-318]

Referent	121 [58-297]	153 [87-327]	153 [87-327]
Exposure	134 [58-318]	142 [58-310]	142 [58-310]

- For canagliflozin vs. 2nd generation SUs

Median Follow-Up Time (Days) [IQR]			
Patient Group	Optum	Marketscan	Medicare
Overall Patient Population	141 [63-336]	159 [83-358]	172 [90-373]
Referent	140 [75-330]	200 [118-414]	200 [118-414]
Exposure	141 [58-341]	144 [62-327]	144 [62-327]

- Report risk per 1,000 patients

Action report name:

- For canagliflozin vs. DPP4i

Optum- <https://bwh-dope.aetion.com/#/projects/details/660/results/34590/result/0>

Marketscan- <https://bwh-dope.aetion.com/#/projects/details/661/results/34591/result/0>

Medicare- <https://bwh-dope.aetion.com/#/projects/details/662/results/34592/result/0>

- For canagliflozin vs. 2nd generation SUs

Optum- <https://bwh-dope.aetion.com/#/projects/details/660/results/34596/result/0>

Marketscan- <https://bwh-dope.aetion.com/#/projects/details/661/results/34597/result/0>

Medicare- <https://bwh-dope.aetion.com/#/projects/details/662/results/34598/result/0>

Date conducted: 04/25/2019

For canagliflozin vs. DPP4i

	Optum	Marketscan	Medicare
Risk per 1,000 patients	7.58	7.81	22.56

For canagliflozin vs. 2nd generation SUs

	Optum	Marketscan	Medicare
Risk per 1,000 patients	9.71	9.39	27.67

10. Final Power Assessment

Date conducted: 12/01/2019

- Re-calculate power in the appropriate excel table, using the revised number of matched patients from the PS-match in Section 9. All other parameters in the table should be the same as in Section 8. If the study is to be implemented in more than one database, copy and paste excel sheet to report power for each database separately and for the pooled analysis that uses data from all databases together. Power calculations are based on the formulas from Chow et al. (2008).

- For canagliflozin vs. DPP4i
 - Pooled

Superiority Analysis		Non-inferiority Analysis	
Number of patients matched		Number of patients matched	
Reference	76,101	Reference	76,101
Exposed	76,101	Exposed	76,101
Risk per 1,000 patients	12.65	Risk per 1,000 patients	12.65
Desired HR from RCT	0.86	Assumed HR from RCT	1
Alpha (2-sided)	0.05	Alpha (2-sided)	0.05
		Non-inferiority margin	1.3
Number of events expected	1925.3553	Number of events expected	1925.3553
Power	0.911332398	Power	0.999926523

- Optum

Superiority Analysis		Non-inferiority Analysis	
Number of patients matched		Number of patients matched	
Reference	19,532	Reference	19,532
Exposed	19,532	Exposed	19,532
Risk per 1,000 patients	7.58	Risk per 1,000 patients	7.58
Desired HR from RCT	0.86	Assumed HR from RCT	1
Alpha (2-sided)	0.05	Alpha (2-sided)	0.05
		Non-inferiority margin	1.3
Number of events expected	296.10512	Number of events expected	296.10512
Power	0.254449294	Power	0.616911596

▪ Marketscan

Superiority Analysis		Non-inferiority Analysis	
Number of patients matched		Number of patients matched	
Reference	23,168	Reference	23,168
Exposed	23,168	Exposed	23,168
Risk per 1,000 patients	7.58	Risk per 1,000 patients	7.58
Desired HR from RCT	0.86	Assumed HR from RCT	1
Alpha (2-sided)	0.05	Alpha (2-sided)	0.05
		Non-inferiority margin	1.3
Number of events expected	351.22688	Number of events expected	351.22688
Power	0.292672624	Power	0.690943556

▪ Medicare

Superiority Analysis		Non-inferiority Analysis	
Number of patients matched		Number of patients matched	
Reference	33,401	Reference	33,401
Exposed	33,401	Exposed	33,401
Risk per 1,000 patients	22.56	Risk per 1,000 patients	22.56
Desired HR from RCT	0.86	Assumed HR from RCT	1
Alpha (2-sided)	0.05	Alpha (2-sided)	0.05
		Non-inferiority margin	1.3
Number of events expected	1507.05312	Number of events expected	1507.05312
Power	0.833370249	Power	0.999133759

- For canagliflozin vs. 2nd generation SUs

- Pooled

Superiority Analysis		Non-inferiority Analysis	
Number of patients matched		Number of patients matched	
Reference	68,850	Reference	68,850
Exposed	68,850	Exposed	68,850
Risk per 1,000 patients	15.59	Risk per 1,000 patients	15.59
Desired HR from RCT	0.86	Assumed HR from RCT	1
Alpha (2-sided)	0.05	Alpha (2-sided)	0.05
		Non-inferiority margin	1.3
Number of events expected	2146.743	Number of events expected	2146.743
Power	0.937493971	Power	0.999980899

- Optum

Superiority Analysis		Non-inferiority Analysis	
Number of patients matched		Number of patients matched	
Reference	16,740	Reference	16,740
Exposed	16,740	Exposed	16,740
Risk per 1,000 patients	9.71	Risk per 1,000 patients	9.71
Desired HR from RCT	0.86	Assumed HR from RCT	1
Alpha (2-sided)	0.05	Alpha (2-sided)	0.05
		Non-inferiority margin	1.3
Number of events expected	325.0908	Number of events expected	325.0908
Power	0.274612159	Power	0.657366306

▪ Marketscan

Superiority Analysis		Non-inferiority Analysis	
Number of patients matched		Number of patients matched	
Reference	23,265	Reference	23,265
Exposed	23,265	Exposed	23,265
Risk per 1,000 patients	9.39	Risk per 1,000 patients	9.39
Desired HR from RCT	0.86	Assumed HR from RCT	1
Alpha (2-sided)	0.05	Alpha (2-sided)	0.05
		Non-inferiority margin	1.3
Number of events expected	436.9167	Number of events expected	436.9167
Power	0.350813593	Power	0.782915462

▪ Medicare

Superiority Analysis		Non-inferiority Analysis	
Number of patients matched		Number of patients matched	
Reference	28,845	Reference	28,845
Exposed	28,845	Exposed	28,845
Risk per 1,000 patients	27.67	Risk per 1,000 patients	9.39
Desired HR from RCT	0.86	Assumed HR from RCT	1
Alpha (2-sided)	0.05	Alpha (2-sided)	0.05
		Non-inferiority margin	1.3
Number of events expected	1596.2823	Number of events expected	541.7091
Power	0.853826925	Power	0.86285876

- Stop analyses until balance and final power assessment are reviewed by primary investigators, FDA, and assigned members of advisory board. Reviewers evaluate the results of the analyses described above in Sections 9 and 10, including numbers of patients, balance in patient characteristics, follow-up time, and reasons for censoring by treatment group, as well as overall rates of outcomes and study power.

Reviewed by PI:	[name]	Date reviewed:	12/9/19
Reviewed by FDA:	[name]	Date reviewed:	12/20/19
Reasons for stopping analysis (if required):			

11. Study Confidence and Concerns

Deadline for voting on study confidence and listing concerns: 12/20/19

- If final feasibility and power analyses are reviewed and approved, proceed to the remaining protocol steps.
- All study team and advisory board members that review this protocol should at this stage provide their level of confidence for the success of the RWD study in the [Google Form](#). This form also provides space for reviewers to list any concerns that they feel may

contribute to a failure to replicate the findings of the RCT, including differences in study populations, poor measurement of study variables, or residual confounding. All responses will be kept confidential and individual-level results will only be shared with the individual respondent.

12. Register study protocol on clinicalTrials.gov

Date conducted:

- Register the study on [clinicalTrials.gov](https://clinicaltrials.gov) and upload this document.

13. Comparative Analyses

Action report name:

Date conducted:

13.1 For primary analysis:

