Appendix A

Mortality- Dependent on data source.

1. All-cause mortality / inpatient mortality

Identified using the vital status file-

Medicare

Identified using the discharge status codes-

Optum-

- 20 = EXPIRED
- 21 = EXPIRED TO BE DEFINED AT STATE LEVEL
- 22 = EXPIRED TO BE DEFINED AT STATE LEVEL
- 23 = EXPIRED TO BE DEFINED AT STATE LEVEL
- 24 = EXPIRED TO BE DEFINED AT STATE LEVEL
- 25 = EXPIRED TO BE DEFINED AT STATE LEVEL
- 26 = EXPIRED TO BE DEFINED AT STATE LEVEL
- 27 = EXPIRED TO BE DEFINED AT STATE LEVEL
- 28 = EXPIRED TO BE DEFINED AT STATE LEVEL
- 29 = EXPIRED TO BE DEFINED AT STATE LEVEL
- 40 = EXPIRED AT HOME (HOSPICE)
- 41 = EXPIRED IN A MEDICAL FACILITY (HOSPICE)
- 42 = EXPIRED - PLACE UNKNOWN (HOSPICE)

Truven-

- 20 - Died
- 22 - Died
- 23 - Died
- 24 - Died
- 25 - Died
- 26 - Died
- 27 - Died
- 28 - Died
- 29 - Died
- 40 - Other died status or Expired at home (Hospice claims only) (depends on year)

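### ITT follow-up still stops at nursing home admission, and for all-cause mortality in Medicare the stated data-loss reason does not justify it

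*Combined protocol and SAP*

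**What the plan says.** Section 6.3.2 lists the events that end as-treated follow-up. One is nursing home admission: "Nursing home admissions are considered a censoring event because the data sources utilized typically provide little to no data on a patient". The sentence goes on to single out drug data: what remains is "little to no data on a patient, particularly on drug utilization, after admission". Nursing home status is also announced as a reason to leave patients out at entry: "We will utilize this as an exclusion reason for cohorts for the same reason".

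Both the as-treated and the ITT analyses are run "with treatment defined as the index drug on the day of cohort entry", and the as-treated analysis is primary. For ITT, "the censoring based on the augmentation/switching and treatment discontinuation will be replaced with a maximum allowed follow-up time of 365 days". Nothing else in the list is altered.

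The source of deaths differs by database. For the commercial databases, section 6.3.1 says: "All-cause inpatient mortality identified using discharge status codes will be used as a proxy for" CV mortality. The mortality sheet in Appendix A gives discharge status code lists for Optum and Truven (read here as MarketScan). For Medicare it says: "Identified using the vital status file".

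The reasons-for-censoring table in section 9 has no line for nursing home admission alone. In the primary comparison the line is "Switch to other DPP4i (for censoring) + nursing home admission"; the sulfonylurea table has the corresponding merged line.

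**The concern.** All-cause mortality is among the secondary outcomes in 6.3.1. Censoring at an event is harmless only if patients censored there have the same later hazard as those who stay under observation. Matched Medicare patients have a mean age of about 71, and nursing home admission in such patients plausibly marks decline and a raised risk of death. If so, the rule removes follow-up selectively. A difference between arms in admission, or in survival after it, would not be seen.

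ITT is also the natural check on informative censoring in the as-treated analysis, and section 13 lists no analysis with a different censoring scheme. An ITT mortality result that keeps a health-related censoring rule is a weaker check than its name suggests.

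**Working it through.** **Step 1. What the ITT rule leaves in place (6.3.2).**

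| Event ending follow-up | As-treated | ITT, by the wording |
|---|---|---|
| Outcome, death, end of enrolment, end of study period | yes | yes |
| Nursing home admission | yes | yes, not named in the replacement |
| Discontinuation plus grace period | yes | removed |
| Switching or augmentation | yes | removed |
| Day 365 | no | added |

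**Step 2. Does the stated reason reach each outcome?** Treatment is fixed at the index drug, so loss of drug data after entry is irrelevant to ITT. What matters is whether outcome data are lost.

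| Outcome | Source | Can data loss justify ITT censoring? |
|---|---|---|
| MI, stroke (all databases) | inpatient diagnosis codes | yes, it can |
| Death in Optum and MarketScan | discharge status codes | yes, it can |
| All-cause death in Medicare | vital status file | no reason given that applies |

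Nothing in the documents says that the vital status file stops at nursing home admission. That it records deaths whatever the care setting is an inference from the kind of source, not a statement in the plan.

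**Step 3. Can the effect be sized?** The plan gives no figure for nursing home censoring. The nearest inputs are the two censoring tables in section 9, which are internally consistent:

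- DPP4i comparison: 589 + 6,913 + 98,215 + 22,353 + 19,170 + 4,962 = 152,202 = 2 × 76,101.
- Sulfonylurea comparison: 548 + 6,001 + 85,900 + 22,281 + 18,853 + 4,117 = 137,700 = 2 × 68,850.

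The merged row as a share of each arm:

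- DPP4i: referent 3,814 / 76,101 = 5.01%; canagliflozin 1,148 / 76,101 = 1.51%.
- Sulfonylurea: referent 3,003 / 68,850 = 4.36%; canagliflozin 1,114 / 68,850 = 1.62%.

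These are upper bounds for nursing home censoring under as-treated follow-up. They do not size the ITT effect in Medicare, for three reasons:

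- They pool three databases. Medicare is 33,401 / 76,101 = 43.9% of matched patients per arm in the first comparison and 28,845 / 68,850 = 41.9% in the second, and no Medicare-only count is given.
- They are as-treated counts. In the DPP4i comparison 64.53% of patients left at the end of index exposure, and ITT would keep following them up to day 365. The counts are therefore not bounds for ITT.
- They mix nursing home admission with within-class switching in unknown proportion.

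Death risk after admission is not given either. To show how little can be said, assume that 10% to 50% of the DPP4i row is nursing home admission and that 5% to 20% of those patients die in the remaining time. The product runs from 4,962 × 0.10 × 0.05 = 25 to 4,962 × 0.50 × 0.20 = 496 deaths. A twentyfold range that is still pooled and as-treated is not an estimate of the effect.

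**The case against.** The strongest reply is that the protocol's reason is broader than drug data. A reader might infer that patients are censored only because dispensings stop. The text says there is little or no data of any kind, with drug use as the leading example. That reply stands for MI, for stroke and for commercial-database deaths, and it limits the point to Medicare all-cause mortality. The plan also says the loss is typical, so one Medicare file is an exception to the reason rather than a refutation of it.

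Second, announcing nursing home status as a cohort exclusion suggests a community-dwelling target population, with which censoring at admission is consistent. This has some force. However, neither flowchart nor the Appendix A criteria show the exclusion, and a restriction at entry does not by itself justify ending ITT mortality follow-up later.

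Third, a reader might divide the canagliflozin counts in the merged row by the recorded deaths (1,148 / 215 = 5.3; 1,114 / 184 = 6.1), or apply a death risk to the whole row, and conclude that uncounted deaths rival counted ones. The documents do not support that. The counts have the limits set out in step 3, and a count in one arm says nothing about the hazard ratio.

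Fourth, a reader might extend the point to MACE. Appendix A words the death component of the primary outcome as inpatient mortality before referring to the mortality sheet. If Medicare MACE counts only inpatient deaths, a death in a nursing home would not enter it even without censoring.

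**Conclusion.** The point holds in a narrow form. By its wording, 6.3.2 censors ITT follow-up at nursing home admission, and for all-cause mortality in Medicare the stated reason does not cover doing so. Deaths between admission and day 365 are lost to that analysis, and the censoring is probably informative. This rests on two assumptions: that the vital status file captures deaths after admission, and that admission is associated with mortality in this population. Both are reasonable, but the documents establish neither.

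Size and direction of any bias cannot be determined. The point affects a secondary outcome, in a non-primary analysis, in one of three databases. It does not show that the as-treated primary analysis, ITT MACE or the commercial-database results are wrong. It is worth acting on because the remedy is cheap and uses data sources already in the plan.

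**What to change.** 1. In 6.3.2, state that for ITT all-cause mortality in Medicare, follow-up is not censored at nursing home admission and runs to death, end of enrolment, end of data or day 365, whichever comes first.
2. Run Medicare ITT MACE without this censoring as a sensitivity analysis only. Note that MI and stroke capture after admission may be less complete, and state whether the Medicare death component is all deaths or inpatient deaths.
3. Keep nursing home censoring in the as-treated analysis, where drug data are needed.
4. In section 9, report nursing home admission separately from within-class switching, by arm and database, subject to the small-cell rules already applied to Medicare.

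The cost is one sentence on mortality, a short note on MACE, Medicare re-runs for the two outcomes and one re-tabulation. The run date in section 13 is blank in the document, so on that showing the change can still be pre-specified.
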